1. OBJECTIVES

1.1 Primary Objectives

1.1.1 Rate of grade 3-5 cisplatin-related adverse events occurring within 90 days of initiation of concurrent radiation and chemotherapy including:

- nausea/vomiting
- ototoxicity
- nephrotoxicity
- neutropenia
- thrombocytopenia

1.1.2 Hypothesis: Patients with locally advanced non-nasopharyngeal SCCHN treated with weekly cisplatin (40 mg/m² weekly for 7 doses) with radiation (RT) will have fewer cisplatin-related acute toxicities as compared to those receiving every three-week cisplatin (100 mg/m² for 3 doses) with radiation in the following cohorts:

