5.2.2 Cisplatin Dosing

Use the actual body weight as long as the BSA is ≤ 2.3 . If the BSA is > 2.3 , recalculate using the adjusted body weight, and use the recalculated BSA to determine the dose with no cap.

Estimate Ideal body weight in (kg)

Males: IBW = 50 kg + 2.3 kg for each inch over 5 feet

Females: IBW = 45.5 kg + 2.3 kg for each inch over 5 feet

Adjusted body weight

$$AjBW = IBW + 0.4(ABW - IBW)$$

Arm 1 – Conventional fractionation plus every 3-week cisplatin

Patients will receive cisplatin (100 mg/m²) administered intravenously over 1 hour on days 1, 22, and 43 of the treatment course, relative to the initiation of radiation.

Arm 2 – Conventional fractionation plus weekly cisplatin

Patients will receive cisplatin (40 mg/m²) administered intravenously over 1 hour on days 1, 8, 15, 22, 29, 36, and 43 of the treatment course, relative to the initiation of radiation.

Premedication: Arms 1 & 2

Suggested premedication: include aprepitant (intravenous or oral), ondansetron, dexamethasone and either promethazine or prochlorperazine, per institutional standard. This trial endorses the NCCN guidelines for anti-emetic prophylaxis.

Pre- and Post-hydration: Arms 1 & 2

Patients must receive vigorous hydration and diuresis. A suggested regimen is: pre-hydration with a 1 liter of normal saline with electrolyte supplementation (e.g. potassium, magnesium) per standard of care, over 2 hours i.v. immediately prior to cisplatin. Then cisplatin 100 mg/m² in 500 ml normal saline is administered over 1 hour. Following cisplatin infusion, an additional 1 liter of normal saline with electrolyte supplementation (e.g. potassium, magnesium) per standard of care, given post-hydration over 2 hours.

Please see Section 6.0 for all dose modifications of cisplatin.

5.3 **Radiation Therapy**

All radiation therapy is considered standard of care, and toxicities and dose modifications will be made by the treating physician based on institutional standards. The guidelines below are recommended practice but may be modified at the discretion of the treating radiation oncologist.

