7.1 Expected Toxicities

7.1.1 Adverse Events List(s)

7.1.1.1 Adverse Event List(s) for Cisplatin

Please see the package insert for all toxicities associated with CISPLATIN. Below is a listing of the most commonly seen toxicities.

Nephrotoxicity: Dose-related and cumulative renal insufficiency, including acute renal failure, is the major dose-limiting toxicity of PLATINOL. Renal toxicity has been noted in 28% to 36% of patients treated with a single dose of 50 mg/m². It is first noted during the second week after a dose and is manifested by elevations in BUN and creatinine, serum uric acid and/or a decrease in creatinine clearance. Renal toxicity becomes more prolonged and severe with repeated courses of the drug. Elderly patients may be more susceptible to nephrotoxicity. Impairment of renal function has been associated with renal tubular damage. The administration of CISPLATIN using a 6-8-hour infusion with intravenous hydration, and mannitol has been used to reduce nephrotoxicity. However, renal toxicity still can occur after utilization of these procedures.

Ototoxicity: Ototoxicity has been observed in up to 31% of patients treated with a single dose of CISPLATIN 50 mg/m² and is manifested by tinnitus and/or hearing loss in the high frequency range (4000 to 8000 Hz). Decreased ability to hear normal conversational tones may occur. Deafness after the initial dose of CISPLATIN has been reported. Ototoxic effects may be more severe in children receiving CISPLATIN. Hearing loss can be unilateral or bilateral and tends to become more frequent and severe with repeated doses. Ototoxicity may be enhanced with prior or simultaneous cranial irradiation. It is unclear whether CISPLATIN-induced

ototoxicity is reversible. Ototoxic effects may be related to the peak plasma concentration of CISPLATIN. Careful monitoring of audiometry is recommended prior to initiation of therapy and prior to subsequent doses of CISPLATIN. Vestibular toxicity has also been reported. Ototoxicity may become more severe in patients being treated with other drugs with nephrotoxic potential.

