Hematologic: Myelosuppression occurs in 25% to 30% of patients treated with CISPLATIN. The nadirs in circulating platelets and leukocytes occur between days 18 to 23 (range 7.5 to 45) with most patients recovering by day 39 (range 13 to 62). Leukopenia and thrombocytopenia are more pronounced at higher doses (>50 mg/m 2). Anemia (decrease of 2 g hemoglobin/100 mL) occurs at approximately the same frequency and with the same timing as leukopenia and thrombocytopenia. Fever and infection have also been reported in patients with neutropenia. Potential fatalities due to infection (secondary to myelosuppression) have been reported. Elderly patients may be more susceptible to myelosuppression. In addition to anemia secondary to myelosuppression, a Coombs' positive hemolytic anemia has been reported. In the presence of cisplatin hemolytic anemia, a further course of treatment may be accompanied by increased hemolysis and this risk should be weighed by the treating physician. The development of acute leukemia coincident with the use of CISPLATIN has been reported. In these reports, CISPLATIN was generally given in combination with other leukemogenic agents.

Gastrointestinal: Marked nausea and vomiting occur in almost all patients treated with CISPLATIN, and may be so severe that the drug must be discontinued. Nausea and vomiting may begin within 1 to 4 hours after treatment and last up to 24 hours. Various degrees of vomiting, nausea and/or anorexia may persist for up to 1 week after treatment. Delayed nausea and vomiting (begins or persists 24 hours or more after chemotherapy) has occurred in patients attaining complete emetic control on the day of CISPLATIN therapy. Diarrhea has also been reported.

OTHER TOXICITIES

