10. STUDY CALENDAR

Baseline evaluations are to be conducted as follows:

- Within 3 weeks prior to registration: Complete history, physical examination, and evaluation of ECOG Performance Status, CBC; serum chemistry tests to include alkaline phosphatase, creatinine, electrolytes, AST (SGOT), and total bilirubin.
- All radiographic studies should be completed within:
 - Cohort 1: 6 weeks prior to registration
 - Cohort 2: 8 weeks prior to registration
- In the event that the patient's condition is deteriorating, laboratory evaluations should be repeated within 48 hours prior to initiation of the next cycle of therapy.

Pre-Study	Wk 1	Wk 2	Wk 3	Wk 4	Wk 5	Wk 6	Wk 7	Post Treatment Follow up	Long term Follow up ^b
Cisplatin Arm 1	A			A			A		
Cisplatin Arm 2	B	B	B	B	B	B	B		
Informed consent	X								
Demographics, medical history	X								
Concurrent meds		X ⁱ							
Physical exam	X	X		X			X	X	X ^h
Pulse, blood pressure	X	X		X			X	X	
Height	X								
Weight ^a	X	X	X ^a	X ^a	X	X ^a	X ^a	X	
Performance status	X	X						X	
CBC w/diff, plts ^a	X	X	X ^a	X ^a	X	X ^a	X ^a	X	X
Serum basic chemistry ^b			X ^a	X ^a		X ^a	X ^a		
Serum comprehensive chemistry ^c	X	X		X			X	X	
Adverse event evaluation		X-----							X
Tumor measurements	X ^d							X ^e	X ^e
B-HCG	X ^f								
Correlative studies		X							
FACTHN and FACT-COG ^g	X ^g						X ^g	X ^g	

A: Arm 1: Cisplatin 100 mg/m² every 3 weeks for 3 total doses

B: Arm 2: Cisplatin 40 mg/m² every week for 7 total doses

a: Every 3 weeks for Arm 1 during radiation, weekly for Arm 2 during radiation, and then as scheduled.

b: Weeks 2,3,5, 6 of Arm 2 only: creatinine, glucose, potassium, sodium.

c: Every three weeks for both arms: Albumin, alkaline phosphatase, total bilirubin, calcium, creatinine, potassium, SGOT [AST], SGPT [ALT], sodium.

- d: Baseline scans can include either: 1) CT with contrast or MRI of the head and neck region, CT of chest or chest x-ray. Response assessment should include assessment of all sites of disease and use the same imaging method as was used at baseline.
- e: Restaging scans must be repeated after the end of protocol treatment within 8 weeks of completion of radiation. Thereafter, scans of the head and neck will be repeated as clinically indicated, but at a minimum of every 6 months (± 6 weeks) for the first two years. Following this, all scans are at the treating physician's discretion.
- f: Serum pregnancy test (women of childbearing potential).

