13. STATISTICAL CONSIDERATIONS

13.1 Study Design/Endpoints

This is a 1:1 randomized, unblinded phase II trial of radiation with cisplatin weekly versus every three weeks for patients with locally advanced non-nasopharyngeal SCCHN. The primary endpoint is cisplatin-related acute toxicities (within the first 90 days after the start of radiation). These include all grade 3-5 events of nausea/vomiting, ototoxicity, nephrotoxicity, and neutropenia and thrombocytopenia. Secondary objectives include clinical outcomes (2-year local control rates, OS, PFS, response), additional toxicity outcomes (rates of dysphagia, dry mouth, and skin, other acute and late events according to CTCAE), correlates (oxidative stress markers), and quality of life outcomes (FACTHN, FACTCOG).

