13.2 Sample Size/Accrual Rate

The primary objective of this study is to see if cisplatin delivered weekly results in fewer cisplatin-related toxicities and improved tolerability compared to cisplatin administered every 3 weeks. Both groups will still receive standard of care radiation therapy in addition to cisplatin. Assuming historical rates of 80% toxicities for patients receiving XRT + cisplatin every 3 weeks [10, 32-34], with 36 patients per arm we will have 80% power based on a Fisher's exact test to detect a decrease in toxicity rate to 50%, assuming a one-sided level of significance equal to 0.05. Conservatively assuming a 10% loss to follow-up, we will recruit 80 total patients for at least 72 analyzable.

Based on the Cancer Research Informatics SRF incidence tables for SCCHN from 2010-2014, **there were an average of 125 patients seen per year at MCC** that would be eligible for this trial based on tumor stage and tumor site. If even 33% of these subjects met all criteria and agreed to participate, we anticipate this study would be completed in 2 years. Our HN CCART has an excellent track record of accrual to clinical trials in this subset of SCCHN, thus we feel that this estimate is conservative and that it is possible that we could accrue faster than predicted.

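### The primary endpoint counts laboratory toxicity to day 90, but no blood test after week 7 has a date, so silent events from the last cisplatin doses can be missed in either arm

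*Combined protocol and SAP*

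**What the plan says.** Section 1.1.1 defines the primary endpoint as "Rate of grade 3-5 cisplatin-related adverse events occurring within 90 days of initiation of concurrent radiation and chemotherapy". Section 13.1 lists the components: "These include all grade 3-5 events of nausea/vomiting, ototoxicity, nephrotoxicity, and neutropenia and thrombocytopenia". The last three normally need a blood test to be seen.

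Section 5.2.2 schedules Arm 1 cisplatin "on days 1, 22, and 43 of the treatment course". Arm 2 is dosed weekly and also ends on day 43.

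In section 10, blood counts and comprehensive chemistry are marked through week 7 and then once more under post-treatment follow-up. The table layout is imperfect in the text available, but the nine blood-count marks fit pre-study, seven treatment weeks and post-treatment. That column carries no day. The footnotes give the following:

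- Footnote a sets the frequency of blood counts during radiation and afterwards refers to a schedule that is not given.
- Footnote c makes comprehensive chemistry three-weekly in both arms, with no stated end, and does not cover the blood count.
- Footnotes e, g and h time the scans, questionnaires and physical examinations. For scans: "Restaging scans must be repeated after the end of protocol treatment within 8 weeks of completion of radiation".

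Section 7.1.1.1 gives the expected timing. For blood counts: "The nadirs in circulating platelets and leukocytes occur between days 18 to 23 (range 7.5 to 45" days), with most patients recovered by day 39. For renal toxicity: "It is first noted during the second week after a dose and is manifested by elevations in BUN and creatinine".

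**The concern.** A rate to day 90 is only as good as the observation to day 90. Here 47 of the 90 days (days 44-90) carry one blood count with no date. Symptomatic toxicity will surface without a scheduled visit; a silent fall in neutrophils or platelets, or a silent rise in creatinine, will not. If the calendar lets a compliant site draw no blood while the last doses act, the reported toxicity rates can be too low. If the shortfall differs between arms, the primary comparison is biased as well. The planned power is only just above 80%, so there is little slack.

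**Working it through.** **Plan's own figure.** Inputs from section 13.2: 80% v 50%, 36 per arm, one-sided 0.05, Fisher's exact test. Summing the two binomial probabilities over every table whose one-sided Fisher p-value is at most 0.05 gives power 0.809. The plan's 80% is reproduced.

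**Timing after a day-43 dose** (dose day plus the offset in section 7.1.1.1):

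- Renal onset, second week after the dose: 43 + 7 to 43 + 14 = about days 50-57.
- Nadir: 43 + 18 to 43 + 23 = days 61-66.
- Most recovered: 43 + 39 = day 82.

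Week 7 is days 43-49. Even a test on its last day precedes all three, and all three fall before day 90.

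**When the undated visit can happen.** Section 5.3.1 allows 30-35 fractions, five a week. Thirty-five uninterrupted fractions end on day 47 (Monday start) or day 49. Adding 8 weeks (56 days) for restaging gives days 103-105, after usual recovery and after the window has closed. A visit in the first days after radiation comes before day 61. Both comply with the calendar.

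**Who receives the day-43 dose.** Thirty uninterrupted fractions end on day 40 or 42, and section 6 allows no chemotherapy once radiation is complete. Those patients have no day-43 dose. In Arm 1 the last dose is then day 22, with nadir on days 40-45, which a week-7 test can meet. In Arm 2 it is day 36, with nadir on days 54-59, which a week-7 test cannot.

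**Share of full planned dosing whose nadir period opens after the last dated test:**

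| Last test | Arm 1 | Arm 2 |
|---|---|---|
| Day 43 | day-43 dose: 100/300 = 33% | day 29, 36 and 43 doses (open days 47, 54, 61): 120/280 = 43% |
| Day 49 | 100/300 = 33% | day 36 and 43 doses: 80/280 = 29% |

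**Effect on the comparison.** Observed rate = true rate minus points missed. A patient is missed only if no other qualifying event was recorded by day 90. The documents give no such rate, so the losses below are assumptions.

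| Points missed, Arm 1 / Arm 2 | Observed rates | Power |
|---|---|---|
| 0 / 0 | 80% v 50% | 0.809 |
| 5 / 5 | 75% v 45% | 0.799 |
| 10 / 10 | 70% v 40% | 0.795 |
| 5 / 0 | 75% v 50% | 0.651 |
| 10 / 5 | 70% v 45% | 0.647 |
| 5 / 10 | 75% v 40% | 0.902 |
| 0 / 5 | 80% v 45% | 0.908 |

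The values above 0.809 are not gains. They arise because the weekly arm's toxicity is under-counted and the apparent difference exceeds the true 30 points.

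**The case against.** Several objections have weight.

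- **Adverse events are collected continuously in section 10, and section 5.6 follows toxicity for 2 years.** This stands for symptomatic events. It does not produce a blood result.
- **Footnote c, read literally, continues three-weekly chemistry, which would put a creatinine at 43 + 21 = day 64.** That reading is possible, but the footnote has no end date, the calendar shows no such visit, and blood counts are not covered.
- **Footnote g dates another contact, at 3 months ± 6 weeks from treatment start.** True, but with 3 months taken as 91 days that is about days 49-133, and it concerns questionnaires.
- **A late test may still detect the event.** The stated recovery range runs to 62 days (43 + 62 = day 105), and renal toxicity is described as more prolonged with repeated courses. This limits the loss. But an abnormality first seen after day 90 cannot be dated inside the window.
- **Clinicians will test anyway.** Probably often. However, "This is a 1:1 randomized, unblinded phase II trial", so leaving tests to discretion lets ascertainment differ by arm.

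A reader might go further and infer that the missed events fall mostly in Arm 1, so that the trial is biased against its own hypothesis. In favour, the last single dose is 100 v 40 mg/m², and section 7.1.1.1 says cytopenia is more pronounced above 50 mg/m². Against, both arms stop on day 43 with the same undated visit, renal toxicity is described as cumulative as well as dose-related with similar planned totals (300 v 280 mg/m²), and the dosing shares above favour neither arm consistently. The documents do not settle the direction. The different test frequency during radiation is a separate matter and is not counted here.

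**Conclusion.** The gap is real. A site can follow section 10 exactly and have no blood test across the protocol's own renal-onset and nadir periods for the last doses, so the primary endpoint can be under-counted in both arms. The day-43 figures apply to patients who receive that dose; for an uninterrupted 30-fraction course the nadir gap remains in Arm 2 only, provided the week-7 test is taken.

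The size and direction of any bias are unknown. Power is nearly unchanged (0.795-0.799) if 5-10 points are lost equally, although both reported rates would then be too low. It falls to 0.651 if 5 points are lost in Arm 1 only. A 5-point loss in Arm 2 only would exaggerate the benefit of weekly dosing (0.908). These figures rest on the plan's 80% v 50% and on assumed losses, and they show sensitivity rather than an expected result. The change is worth making because the endpoint is primary and the cost is small.

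**What to change.** In section 10:

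- Give the existing post-treatment blood count, comprehensive chemistry and adverse event review a fixed window counted from treatment start, the same in both arms, inside the 90 days and covering the stated nadir period. About day 64 ± 4 (days 60-68) would cover days 61-66.
- State whether the three-weekly chemistry in footnote c continues to that visit. A window at day 64 follows the stated renal onset, so it detects renal injury that persists; a rise that resolves before about day 60 would still be missed.
- Record adverse events through day 90 in both arms, sharing the restaging visit where the dates coincide.

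The visit and its tests are already in the calendar. The cost is a revised footnote, a tighter visit window and possibly one extra contact near day 90. No dose or treatment rule changes.

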1.2 Secondary Objectives

1.2.1 To compare the following therapeutic endpoints in both populations:

- 2-year local control rates
- Overall survival (OS)
- Progression free survival (PFS)
- Response Rate (Cohort 1 only, as Cohort 2 is completely resected)

1.2.2 To compare and contrast the development of oxidative stress markers which occur as a result of exposure to weekly or every 3-week doses of cisplatin in this population

1.2.3 Rates of radiation related CTCAE adverse events, specifically: mucositis, dysphagia, dry mouth, and skin and their relationships with patient reported outcomes at 3 months and 12 months

1.2.4 CTCAE acute (< 90 days from start of chemoradiation) adverse events related (possibly, probably or definitely) to cisplatin or radiation

- 1.2.5 CTCAE late (> 90 days from start of chemoradiation) adverse events related (possibly, probably or definitely) to cisplatin or radiation.
- 1.2.6 Quality of life as measured by Functional Assessment of Cancer Therapy-Head & Neck (FACTHN) and Functional Assessment of Cancer Therapy Cognition (FACTCOG) at baseline, 3, and 12 months from end of RT

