5.3.1 Dose Specifications

IMRT has been a standard of care in the U.S. beginning in 2005 and is now widely used in practice. Use of H&N IMRT in RTOG protocols (and associated QA) was begun in 2005 in RTOG 0522, as an optional technique. At the close of the accrual phase, approximately 90% of cases enrolled on 0522 (>800 patients) were treated with IMRT. Oropharynx cases comprised 70% of the study population.

IMRT will be delivered in 30-35 fractions over 6-7 weeks, 5 fractions weekly. The primary tumor and involved nodes (CTV1) will typically consist of a 0.5-1.5 cm expansion of the gross tumor volume (GTV) to cover potential local invasion and will be prescribed 2 Gy/fraction, total 55-70Gy. High-risk sub-clinical disease sites, which include possible local subclinical infiltration at the primary site (primary site CTV2) and first echelon nodes, which are not clinically or radiographically involved (nodal CTV2), should be expanded by 3-5 mm to create PTV2. PTV2 should receive 1.6 Gy/fraction to a total dose of 52.8 Gy to 56 Gy. Lower-risk targets (PTV3) (such as neck nodal levels which are not first echelon nodes and are not adjacent to levels containing grossly involved nodes) will be prescribed 50-52.5 Gy. If the low neck is treated, the preferred technique is to treat with isocentric matching AP or AP-PA fields with larynx block, matched to the IMRT portals just above the arytenoids. The dose will be 2 Gy per fraction prescribed to 3 cm depth to a total dose of 50 Gy in 25 daily fractions. Whole-neck IMRT is allowed. This can be achieved by either boosting the low neck field with an additional 16 Gy in 8 fractions, by an AP or AP-PA fields, or by planning the whole neck using IMRT. In cases of gross involvement of the vallecula or low neck, whole-neck IMRT should be considered. Whole-neck IMRT may also be considered if level VI is considered to be at risk due to gross involvement of level IV nodes. All plans must be normalized such that 95% of the volume of the PTV is covered with prescription dose.

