5.3.2 Compliance Criteria

Treatment breaks must be clearly indicated in the treatment record along with the reason(s) for the treatment break(s). Treatment breaks, if necessary, ideally should not exceed 5 treatment days at time and 10 treatment days total. Treatment breaks should be allowed only for resolution of severe acute toxicity and/or for intercurrent illness and not for social or logistical reasons. Any treatment break(s) exceeding 2 treatment days for reasons other than toxicity/illness will be considered a protocol deviation. The following define compliance:

Overall RT treatment time:

- ≤ 52 days (compliant)
- > 52 days (non-compliant)
- Up to 57 days for non-medical reasons (such as holiday, machine breakdown) as determined by the treating radiotherapy physician

Missed treatments due to holidays or logistic reasons can be compensated for by delivering an additional BID treatment during the week, OR treating on the Saturday or Sunday of that week, OR adding to the end of treatment. These additions will not be considered non-compliance.

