- g: Pre-study, at 3 months (± 6 weeks) and 12 months (± 12 weeks) following initiation of treatment.
- h: Physical exams will be repeated as clinically indicated, but at a minimum of every 6 months (± 6 weeks) for the first two years. Following this, all follow-up is at the treating physician's discretion.
- i: Only on Days 1 and 2 of cycle 1

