12.1.1 Method

This study will require data submission and reporting via the OnCore Database, which is the official database of the Markey Cancer Center Clinical Research Office (CRO). Instructions for submitting data are listed in Study-Specific Data Management Plans created by Data Management Specialist Senior housed in the Cancer Research Informatics (CRI) Shared Research Facility (SRF). **Please refer to the study calendar for all data reporting requirements.**

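### The quality-of-life forms are timed from end of RT in objective 1.2.6 but from start of treatment in calendar footnote g, and the head and neck form supplied is the HNSI, not the FACTHN that is named

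*Combined protocol and SAP*

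**What the plan says.** **Timing.** Objective 1.2.6 (section 1.2) places FACTHN and FACTCOG "at baseline, 3, and 12 months from end of RT". Footnote g to the study calendar (section 10) places the same forms "Pre-study, at 3 months (± 6 weeks) and 12 months (± 12 weeks) following initiation of treatment". Objective 1.2.3 also relies on patient-reported scores, relating them to "mucositis, dysphagia, dry mouth, and skin and their relationships with patient reported outcomes at 3 months and 12 months", but gives no starting point for those months. Section 13.4 plans repeated-measures mixed models for quality of life over time and names no time origin. Section 12.1.1 tells staff: "Please refer to the study calendar for all data reporting requirements".

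**Radiation duration.** Section 5.3.1 states: "IMRT will be delivered in 30-35 fractions over 6-7 weeks, 5 fractions weekly". Section 5.3.2 counts an overall time of up to 52 days as compliant, allows up to 57 days for non-medical reasons, and says breaks should ideally total no more than 10 treatment days. Section 5.3 adds: "The guidelines below are recommended practice but may be modified at the discretion of the treating radiation oncologist". Section 5.2.1 has cisplatin and radiation start on the same day, give or take one day.

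**Instrument.** Objective 1.2.6, the calendar and section 13.1 all name FACTHN. Section 9.1 describes FACT-Cog only. Appendix C, the only head and neck questionnaire supplied or listed in the contents, is titled FACT/NCCN HNSI.

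**The concern.** Two parts of the protocol define the same visit from different starting points, and those points are a whole radiation course apart. Loose drafting does not explain this. Objectives 1.2.4 and 1.2.5 count from the start of chemoradiation, so the list of objectives uses both clocks and 1.2.6 uses end of radiation. The calendar also uses both: footnote e says "Restaging scans must be repeated after the end of protocol treatment within 8 weeks of completion of radiation", so its authors named radiation completion where they meant it.

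At stake is what a reported 3-month score describes. A form completed several weeks after radiation and one completed three months after it answer different questions about recovery. A reader of the results could not tell which was meant, nor which questionnaire lay behind a result labelled FACTHN.

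**Working it through.** The plan gives no figure of its own here, so the check is date arithmetic.

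**Inputs.** Three months = 3 × 365.25/12 = 91.3 days = 13.0 weeks; 12 months = 365.25 days = 52.2 weeks (conventions). Start of treatment is taken as start of radiation (section 5.2.1). Radiation durations: 6 and 7 weeks (section 5.3.1); 52 days = 7.4 weeks and 57 days = 8.1 weeks (section 5.3.2). As an extended case, 35 fractions plus 10 break days makes 45 weekdays, or 9 weeks. That exceeds the 52-day compliance limit, but section 5.3.2 contemplates breaks of that length.

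**Formulas, with D the radiation duration in weeks.**

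- On-schedule 3-month form, weeks after radiation = 13.0 − D.
- Calendar window from start = 13.0 ± 6 = 7.0 to 19.0 weeks; its opening relative to end of radiation = 7.0 − D.
- Objective's 3-month point from start = D + 13.0, compared with the close at 19.0.
- Objective's 12-month point from start = D + 52.2, compared with the window 52.2 ± 12 = 40.2 to 64.2.

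| D (weeks) | 3-month form, weeks after RT | Window opens, weeks from end of RT | Objective's 3-month point, weeks from start (close 19.0) | Objective's 12-month point, weeks from start (close 64.2) |
|---|---|---|---|---|
| 6.0 | 7.0 | +1.0 | 19.0 | 58.2 |
| 7.0 | 6.0 | 0.0 | 20.0 | 59.2 |
| 7.4 | 5.6 | −0.4 | 20.5 | 59.6 |
| 8.1 | 4.9 | −1.1 | 21.2 | 60.3 |
| 9.0 | 4.0 | −2.0 | 22.0 | 61.2 |

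The objective asks for 13.0 weeks after radiation. By construction the on-schedule form is early by D, at 3 months and at 12 months alike. The windows differ in effect: ± 12 weeks exceeds every D considered, while ± 6 weeks only equals the shortest.

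**Sensitivity.** Calendar months vary in length, so the 6-week row is a borderline case. With actual calendar months, no holidays, and every weekday start from May 2018 to April 2021 (assumed dates), the objective's 3-month point ran from 5 days before the close to 2 days after it for 30 uninterrupted fractions (about 7% of starts fell past it), and from 2 to 9 days after it for 35. Hence the wording: near the edge for 6 weeks, past it for 7.

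**Instrument.** Appendix C contains 10 items: GP4, GP1, H&N7, H&N12, H&N3, H&N10, GP2, H&N11, GE6 and GF7. No text says that this form is what FACTHN means.

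**The case against.** The strongest reply is that these are two wording slips on outcomes that section 13.4 calls exploratory and mainly descriptive, and that the window is wide enough to absorb much of the difference. The first half stands, and sets the severity. The second half holds at 12 months. At 3 months it holds only in part: for 6-week radiation the objective's point is usually just inside, but for 7 weeks or more it is not.

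Other points for the plan also stand:

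- Radiation may be modified, so the weeks above illustrate the protocol's stated schedules. They are not bounds.
- Section 12.1.1 points to the calendar but also leaves submission instructions to study-specific data management plans that are not in the documents. It is likely, not certain, that collection follows footnote g.
- Nothing shows that form dates go unrecorded, and the compliance rule in section 5.3.2 already requires the radiation end date.

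A reader might infer that the conflict biases the comparison between arms. The documents do not establish that, since footnote g applies one clock to both. They do not exclude some imbalance either: if toxicity breaks differ by arm, time since radiation differs under footnote g, just as the visit date would under an end-of-radiation clock.

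A reader might also infer that the HNSI cannot serve objective 1.2.3 because it has no dry-mouth or skin item. That objective does not require symptom-matched items, and the documents do not list the FACTHN items for comparison.

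**Conclusion.** The point holds as a minor internal inconsistency in two parts. Followed as written, footnote g yields a 3-month form about 6 to 7 weeks after an uninterrupted course, about 5 to 6 weeks after if radiation takes 52 to 57 days, and about 4 weeks after in the extended case, against about 13 weeks in objective 1.2.6. The window can open at or before the end of radiation. The 12-month form is early by a similar number of weeks, but the objective's point remains inside its window for every duration considered. These figures assume that treatment and radiation start together and that forms are completed on schedule; the documents do not say how completion dates will spread across the window.

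Independently of timing, the instrument named and the form supplied do not agree. The effect is confined to the time label and instrument label of exploratory quality-of-life results. Nothing here supports extending it to the primary toxicity endpoint or the sample size, neither of which uses these forms.

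**What to change.** Use one anchor in objectives 1.2.6 and 1.2.3 and in footnote g.

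- **Smaller change:** reword 1.2.6 to initiation of treatment, state the same origin in 1.2.3, and report the 3-month result as early post-radiation. This costs a short wording amendment and no rescheduling. The downside is that the study no longer reports 3 months after radiation.
- **Alternative:** move footnote g to end of radiation. This answers 1.2.6 as worded, but shifts each target date later by the length of radiation (about 6 to 7 weeks if uninterrupted) and makes the visit date depend on radiation duration.

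Under either choice, use the form completion date and the radiation end date in the analysis and report time since radiation by arm, because breaks may differ by arm whichever clock is kept. Forms already collected remain usable if both dates are known.

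Make the instrument name and form agree: rename the endpoint HNSI in 1.2.6, the calendar and section 13.1, or supply the FACTHN. The first is a text correction; the second replaces one questionnaire, and forms already completed on the HNSI would need to be reported under that name.
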